1.5. Study Conduct

This study will be conducted in compliance with the protocol approved by the Institutional Review Board (IRB) or Independent Ethics Committee (IEC) and in accordance with Good Clinical Practice (GCP) standards.

2. STUDY OBJECTIVES AND ENDPOINTS

Objectives	Endpoints			
Primary				
To assess the safety and tolerability of ≤ 5 treatment cycles of dinutuximab beta in combination with 13-cis-retinoic acid (RA) as maintenance therapy in Chinese patients with high-risk neuroblastoma	Adverse events (AEs) characterized by type, frequency, severity (as graded by the National Cancer Institute-Common Terminology Criteria for Adverse Events [NCI-CTCAE] version 5.0), timing, seriousness, and relationship to study drug(s); and other safety assessments			
To characterize the pharmacokinetics (PK) of dinutuximab beta in Chinese patients	PK parameters of dinutuximab beta, including but not limited to area under the concentration-time curve (AUC), maximum serum concentration (C_{max}), minimum serum concentration (C_{min}), time to C_{max} (t_{max}), and half-life ($t_{1/2}$), if data permits.			
Exploratory				
To explore the preliminary anti-tumor activity and event free survival rate (EFS), of ≤ 5 treatment cycles of dinutuximab beta in combination with 13-cis-RA as maintenance therapy in Chinese patients with high risk neuroblastoma, if applicable	EFS is defined as the time from initiating study drug(s) to disease progression, death from any cause, relapse, secondary malignancy as assessed by investigators, including EFS rate at 6 months as measured by Kaplan-Meier method			

3. STUDY DESIGN

3.1. Summary of Study Design

This is an open-label, multi-center, single-arm, Phase 1 study evaluating the safety and pharmacokinetics of dinutuximab beta as maintenance therapy in Chinese patients with high-risk neuroblastoma.

Potential patients will be screened for eligibility before study enrollment (screening period ≤ 28 days). The study will recruit approximately 8 patients who will be hospitalized (with a full resuscitation equipment) on Day 1 of each cycle and will receive continuous infusion of dinutuximab beta administered at a dose of 10 mg/m²/day for 10 consecutive days in 35-day cycles (total dose 100 mg/m²/cycle). Patients must be administered in a unit with a full resuscitation equipment. Patients will be discharged from the hospital at the investigator's discretion. Patients will continue to receive 13-cis-RA 160 mg/m²/day, divided into close to 2 equal doses and given orally twice a day for 14 days after completion of dinutuximab beta infusion.

[figure not shown]
Patients may receive up to five 35-day cycles in the absence of relapse, disease progression or unacceptable toxicity.

Refer to Figure 1 for an overview of the study design and Appendix 1 for details on study assessments and procedures that will be carried out during the study.

The maximum duration of participation (Screening Visit to Safety Follow-up Visit) for individual patients will be approximately 35 weeks. Each patient will participate in the screening period (\leq 28 days), study intervention infusion period (\leq 25 weeks), and a post-infusion period (\leq 6 weeks). Additional clinical follow-up might be needed depending on findings during the study.

Figure 1: Study Schema

- Dinutuximab beta intravenous infusion (continuous infusion from Day 1 to Day 11 of each cycle)
- 13-cis-retinoic acid orally twice a day for 14 days, starting from the next day after completion of dinutuximab beta (Day 12 to Day 25) in each cycle

Abbreviations: EOT, end of treatment; PK, pharmacokinetic(s).

All patients will be closely monitored for AEs throughout the study and for 40 days after the last dose of study drug. AEs will be graded according to the NCI-CTCAE version 5.0. Refer to Section 9 for additional and specific information regarding AE monitoring and reporting.

PK analysis will be performed for dinutuximab beta.

Tumor assessments or monitoring will be performed by the investigators at Screening Visit, end of treatment Cycle 3, and end of treatment Visit per their clinical practice. International Neuroblastoma Response Criteria (INRC) (Brodeur et al 1993) is recommended as a reference for response evaluation (Section 8.4) in patients evaluable for tumor assessment. Refer to Section 7.6 for additional considerations regarding treatment continuation and withdrawal. Patients who, at the time of progression, have an ongoing AE that leads to treatment discontinuation and who have completed the scheduled Safety Follow-up Visit will be followed up until the event resolves, the investigator assesses the event as stable, the patient is lost to follow-up, or the patient starts a new anticancer therapy, end of study, whichever comes first.

Patients who have discontinued study drug(s) should return to the site for an End-of-Treatment (EOT) Visit as detailed in Section 7.4. After the EOT Visit, patients will have scheduled follow-up visits for safety (Appendix 1).

Study procedures and assessments are further detailed in Section 7 and Section 8, respectively, and the Schedule of Assessments can be found in Appendix 1.

4. STUDY POPULATION

The specific eligibility criteria for selection of patients are provided in Section 4.1 and Section 4.2. The sponsor will not grant any eligibility waivers.

4.1. Inclusion Criteria

Each patient must meet all the following inclusion criteria to be considered eligible for participation in this study:

- 1. Signed informed consent form (ICF) and ability to comply with study requirements: patient or his/her parent/guardian must be capable of giving signed informed consent/assent as described in Section 14.3 including compliance with the requirements and restrictions listed in the ICF and in this protocol.
- 2. Age \geq 12 months at consent
- 3. Diagnosis of high-risk neuroblastoma according to the International Neuroblastoma Staging System (INSS) criteria, ie, INSS Stage 4 without *MYCN* amplification (MNA) and aged ≥ 18 months; or INSS Stage 2-4 with MNA
- 4. Patients who have previously received induction chemotherapy and achieved a partial or complete response followed by myeloablative therapy and stem cell transplantation. Stem cell transplantation should be completed within 120 days of dinutuximab beta first administration. The date patients complete the last stem cell transplantation is defined as day zero (Day 0).
- 5. Not receiving standard or experimental treatments within 2 weeks before study treatment start and full recovery from the short-term major toxic effects of any prior treatment
- 6. Consistency of contraceptive use by men or women with local regulations regarding the methods of contraception for those participating in clinical studies
 - NOTE: The reliability on sexual abstinence for male and/or female enrollment eligibility needs to be evaluated in relation to **the duration of the clinical study and the preferred and usual lifestyle of the patient**. Periodic abstinence (eg, calendar, ovulation, symptothermal, or postovulation methods) and withdrawal are not acceptable methods of contraception.
- 7. Females of childbearing potential must be willing to use a highly effective method of birth control for the duration of the study, and 180 days after the last dose of study drug(s), and have a negative urine or serum pregnancy test ≤ 7 days of the first dose of study drug(s) (Appendix 4).
- 8. Nonsterile males must be willing to use highly effective method of birth control for the duration of the study and for 180 days after the last dose of study drug(s) (Appendix 4).
 - A sterile male is defined as one for whom azoospermia has been previously demonstrated in a semen sample examination as definitive evidence of infertility.
 - Males with known "low sperm counts" (consistent with "subfertility") are not to be considered sterile for purposes of this study.

- 9. Life expectancy of \geq 12 weeks
- 10. Performance status \geq 70% (Lansky Score or Karnofsky, see Appendix 3)
- 11. Laboratory tests:
 - ANC $\geq 1.5 \times 10^9$ /L, platelets $\geq 100 \times 10^9$ /L, and hemoglobin > 80 g/L
 - ALT and AST \leq 2.5 x upper limit of normal (ULN) or < 5 x ULN if hepatic metastases are present; and total bilirubin < 1.25 x ULN
 - Creatinine clearance or radioisotope glomerular filtration rate (GFR) > 60 mL/min/1.73m²
- 12. Negative test for hepatitis B surface antigen (HBsAg).
- 13. Pulse oximetry > 94% on room air

4.2. Exclusion Criteria

Patients who meet any of the following criteria will be excluded from this study:

- 1. Hypersensitivity to ≥ 1 component of dinutuximab beta antibody or against mouse proteins
- 2. Actively progressive disease (not stabilized) or recurrent disease at the time of inclusion into the study
- 3. Significant intercurrent illnesses and/or any of the following:
 - Symptoms of congestive heart failure or uncontrolled cardiac rhythm disturbance
 - Significant psychiatric disabilities or uncontrolled seizure disorders
 - Active infections or active peptic ulcer, unless these conditions are corrected or controlled
 - Clinically significant neurologic deficit or objective peripheral neuropathy (> Grade 2)
 - Clinically significant, symptomatic pleural effusions
- 4. Previous treatment with anti-GD2 antibody before enrolling in this study
- 5. Any condition that required systemic treatment with either corticosteroids or other immunosuppressive medication \leq 14 days before the first dose of study drug(s).
- 6. Concurrent treatment with any non-study anticancer therapies
- 7. Patients with active hepatitis C infection should be excluded. Note: Cured hepatitis C patients (as defined by a positive hepatitis C virus (HCV) antibody test and negative HCV RNA test) can be enrolled
- 8. Known history of HIV infection

5. STUDY TREATMENT

5.1. Formulation, Packaging, and Handling

5.1.1. Dinutuximab Beta

Formulation

Infusion: A volume of 4.5 ± 0.25 mL, which corresponds to a minimum extractable dose of 20 mg/vial, is filled into 6-mL type 1 glass vials.

Table 2: Dinutuximab Beta Formulation

Content	$4.5 \pm 0.25 \text{ mg/mL}$
Buffer	20 mM histidine, 5% sucrose, 0.01% Tween 20, water for injection
рН	5.5-6.5

The vials are closed with halobutyl rubber stoppers and sealed with aluminum flip-off caps. The actual antibody content of the respective batch of dinutuximab beta is indicated on the label on the vials.

Packaging, Labeling, And Handling

Dinutuximab beta will be supplied in a commercial presentation by sponsor.

The contents of the label will be in accordance with all applicable local regulatory requirements. The study drug must be kept at the temperature condition as specified on the label. Refer to the Pharmacy Manual for details regarding administration, accountability, and disposal. Please also refer to Dinutuximab Beta's Prescribing Information for other details regarding Dinutuximab beta.

5.1.2. 13-cis-retinoic acid

The 13-cis-RA (TeeWasH[®]), a liquid-filled capsule, will be supplied by sponsor. Management (ie, handling, storage, administration, and disposal) of 13-cis-RA will be in accordance with relevant local guidelines and/or prescribing information. The contents of the label will be in accordance with all applicable local regulatory requirements.

For the other details regarding 13-cis-RA, please refer to the local label of 13-cis-retinoic acid or Pharmacy Manual accordingly.

5.2. Dosage, Administration, and Compliance

Accurate records of all study drug(s) received, dispensed, returned, and disposed of should be maintained in the site's Drug Inventory Log. Refer to the Pharmacy Manual for details of study drug management, drug preparation, storage, and administration.

5.2.1. Dinutuximab Beta

Dosage

Total dose: 100 mg/m²/cycle

Patients may receive up to five 35-day cycles in the absence of disease progression or unacceptable toxicity.

Dinutuximab beta is administered at a dose of 10 mg/m²/day as a 24-hour continuous infusion for 10 days (total dose 100 mg/m²/cycle) for five 35-day cycles.

Preparation of Infusion

The solution for infusion must be prepared under aseptic conditions. The solution must not be exposed to direct sunlight or heat.

The patient-specific daily dose of dinutuximab beta is calculated based on BSA. Dinutuximab beta should be diluted aseptically to the patient-specific concentration/dose with sodium chloride 9 mg/mL (0.9%) solution for infusion, containing 1% human albumin (eg, 5 mL of 20% human albumin per 100 mL of 0.9% sodium chloride solution).

For continuous infusions, the solution for infusion can be prepared freshly on a daily basis, or sufficient for up to 5 days of continuous infusion. The daily dose is 10 mg/m². The amount of solution to be infused per day (within a treatment course of 10 consecutive days) should be 48 mL; with 240 mL for a 5-day dose. It is recommended to prepare 50 mL solution in a 50 mL syringe, or 250 mL in an infusion bag suitable for the employed infusion pump, ie, an overfill of 2 mL (syringe) or 10 mL (infusion bag) to allow for dead volumes of the infusion systems.

Administration of The Infusion

The solution for infusion should be administered via a peripheral or central intravenous line. Other intravenously co-administered agents should be delivered via a separate infusion line. The container should be inspected visually for particulates before administration. It is recommended that a 0.22 micrometer in-line filter is used during infusion.

For continuous infusions, any medical device suitable for infusion at a rate of 2 mL per hour can be applied, eg, syringe infusion pumps/infusors, electronic ambulatory infusion pumps. Note that elastomeric pumps are not considered suitable in combination with in-line filters.

The investigator may need to reduce or delay doses or stop treatment if certain side effects occur. It allows the investigator to decrease at 50% of the previous dose or interrupt the infusion. In this instance, the total amount does not need to equal 240 hours of infusion per cycle ideally (total dose of 100 mg/m²/cycle). The investigator must record the reasonable reason for providing any alternative dose during treatment.

Refer to Qarziba EU SmPC for storage of the diluted solution and disposal.

Compliance

Compliance will be assessed by the investigator and/or study personnel at each patient visit along with information provided by the patient and documented accordingly. The investigator and/or

study personnel will keep accurate records of the quantities of agents dispensed and used by each patient. This information must be captured in the source document at the end of each cycle.

5.2.2. 13-cis-retinoic acid

Patients will receive 13-cis-RA (TeeWasH®) at a total daily dose of 160 mg/m²/day, administered in close to 2 equal oral doses twice a day for 14 days after completion of dinutuximab beta infusion. Doses will need to be rounded to the nearest 10 mg. Capsules come as 10 mg sizes and can be emptied into a high fat food such as ice cream or chocolate mousse to administer. Investigators can adjust the dose of 13-cis-RA for the patient's conditions by following the 13-cis-RA prescription or investigators' experience in using 13-cis-RA. If the total daily doses are odd numbers of 13-cis-RA capsules, the number of capsules for each time can be unequal. In that case, if the daily doses are 11 capsules, patients would receive 5 capsules in the morning and 6 capsules in the evening or 6 capsules in the morning and 5 capsules in the evening.

Suggested supportive care for 13-cis-RA:

- Topical vitamin E should be applied to the lips twice a day during 13-cis-RA oral administration therapy if cheilitis develops
- Patients should avoid direct sun exposure while on 13-cis-RA
- Patients should avoid exposure to vitamin A products during 13-cis-RA

5.3. Overdose

In the case of overdose, patients should be carefully observed for signs or symptoms of adverse reactions and supportive care administered, as appropriate.

5.4. Dose Delay or Modification

Dose modification

This protocol allows some alteration from the currently outlined infusion schedule of dinutuximab beta, but the maximum cumulative exposure will not exceed 100 mg/m²/cycle.

Based on the Investigator's evaluation of the severity of adverse drug reactions to dinutuximab beta, patients may undergo a dose reduction of 50% or a temporary interruption of the infusion. As a consequence, either the infusion period is prolonged or, if tolerated by the patient, the infusion rate may be increased up to 3 mL/h (continuous infusion), in order to administer the total dose.

Regarding the dose modification of 13-cis-RA, please refer to local label of 13-cis-retinoic acid.

Table 3: Recommended Dinutuximab Beta Dose Modification

Adverse reaction	Severity	Treatment modification
Any	Grade 1 or 2	Decrease infusion rate to 50%. After resolution, resume infusion at original rate.

Hypersensitivity reaction	eg, Hypotension	Interrupt infusion and administer supportive measures. After resolution, resume infusion at original rate.
Dilated pupils with sluggish light reflex ± photophobia		Interrupt infusion. After resolution, resume infusion at 50% rate.
Any	≥ Grade 3	Interrupt infusion and administer supportive measures. Resume infusion at 50% rate if adverse drug reaction (ADR) resolves or improves to Grade 1 or 2 within 3 days of onset. If 50% dose reduction is tolerated for ≥ 1 day, consider advancing infusion to full rate as tolerated. If toxicity (≥ Grade 3) recurs at 50% dose reduction, treatment should be discontinued. If toxicity (≥ Grade 3) recurs while at 100% infusion rate, stop infusion and reduce dose to 50% if toxicity resolves or improves to ≤ Grade 2 within 3 days of onset. Do not increase dose to 100% again.
Capillary leak syndrome		Interrupt infusion and administer supportive measures. Resume at 50% rate if ADR resolves or improves to Grade 1 or 2.
Capillary leak syndrome requiring ventilator support; allergic reaction (anaphylaxis), skin toxicity, severe neuropathic pain, any other Grade 4 toxicity (which does not recover to Grade 1 or 2 or baseline within 5 weeks)	Grade 4	Discontinue infusion. Contact sponsor to confirm if patient may continue infusion at the start of the subsequent cycle.

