7.6. Discontinuation From Study Treatment or From the Study

7.6.1. Patient Discontinuation From Study Treatment (End of Treatment for an Individual Patient)

Patients have the right to discontinue study drug at any time for any reason. In addition, the investigator has the right to discontinue a patient from study drug at any time. Patients who discontinue study drug for reasons other than relapse or progressive disease (PD) should be followed for assessments of preliminary anticancer activity (Section 8.4) and safety (Section 8.2), if possible.

The primary reason for discontinuation from study drug should be documented on the appropriate eCRF. Patients may discontinue study drug for reasons including but not limited to the following:

- Relapse
- PD
- AE
- Patient decision
- Pregnancy
- Any medical condition that the investigator or sponsor determines may jeopardize the patient's safety if he or she were to continue the study drug
- Use of any concurrent anticancer therapy, including chemotherapy, hormonal therapy, immunotherapy, standard or investigational agents (including Chinese [or other Country] herbal medicine and Chinese [or other Country] patent medicines) for the treatment of cancer [regardless of cancer type])
- Patient noncompliance
 - Study site staff should first counsel patients who are significantly noncompliant (eg, missing 2 treatment cycles) on the importance of study drug compliance and drug accountability. The investigator may, in consultation with the medical monitor, discontinue patients from treatment who are consistently noncompliant.

Treatment with dinutuximab beta should be permanently discontinued if the following toxicities occur:

• Grade 3 or 4 anaphylaxis

- Prolonged Grade 2 peripheral motor neuropathy
- Grade 3 peripheral neuropathy
- Grade 3 vision eye toxicity
- Grade 4 hyponatremia (< 120 mEq/L) despite appropriate fluid management
- Recurrent or Grade 4 capillary leak syndrome (requires ventilator support)

If dinutuximab beta or 13-cis-RA is discontinued permanently before cycle 5 for reasons other than relapse or PD, the other drug could be continued per the study protocol.

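### Table 3 in section 5.4 lets dinutuximab beta resume after reactions that section 7.6.1 treats as permanent stops, and no text says which prevails.

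*Protocol*

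**What the plan says.** Three rows of Table 3 (Protocol 5.4) matter here.

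- **Any reaction, Grade 3 or worse.** Interrupt, give supportive measures, then "Resume infusion at 50% rate if adverse drug reaction (ADR) resolves or improves to Grade 1 or 2 within 3 days of onset". After at least a day tolerated at half rate, full rate may be considered. A recurrence at Grade 3 or worse ends treatment if it happens at half rate. If it happens at full rate, it leads back to half rate, provided that it improves within 3 days.
- **Capillary leak syndrome.** Interrupt, then resume at half rate on resolution or improvement to Grade 1 or 2. First and repeat episodes are not distinguished.
- **Grade 4 row.** The list opens with "Capillary leak syndrome requiring ventilator support; allergic reaction (anaphylaxis" and continues with "skin toxicity, severe neuropathic pain, any other Grade 4 toxicity (which does not recover to Grade 1 or 2 or baseline within 5 weeks" (each quotation stops just before a closing bracket). The action is "Discontinue infusion. Contact sponsor to confirm if patient may continue infusion at the start of the subsequent cycle".

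Section 7.6.1 says: "Treatment with dinutuximab beta should be permanently discontinued if the following toxicities occur". Its list includes "Grade 3 or 4 anaphylaxis", Grade 3 peripheral neuropathy, Grade 3 eye toxicity, and capillary leak syndrome that recurs or reaches Grade 4 with ventilator support. It gives no exception for sponsor agreement. Skin toxicity and neuropathic pain are not on the list.

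Sections 3.1 and 7.3 refer the reader to section 7.6 for further considerations on continuing or withdrawing treatment. They set no order of precedence.

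**The concern.** A permanent stop cannot stand beside a route to restart for the same event. An investigator managing anaphylaxis from Table 3 would reach a different action from one working from 7.6.1. At stake is re-exposure of a child to an antibody after a reaction that the protocol elsewhere treats as ending treatment. Anaphylaxis and capillary leak syndrome are both recognised risks of this drug (sections 1.2.3 and 9.6).

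There are two lesser consequences. Section 15.3 generally bars investigators in China from departing from the protocol without ethics committee and sponsor approval, so following one instruction could be recorded as a deviation from the other. SAP 6.6.2 also counts adverse events leading to discontinuation, reduction and interruption separately. With about 8 patients, one patient handled under a different rule moves a category by 1/8 = 12.5 percentage points.

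**Working it through.** **Step 1. Table 3 against 7.6.1.** No statistical figure is at issue, so the texts are set side by side.

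| Reaction | Table 3 | 7.6.1 |
|---|---|---|
| Grade 4 anaphylaxis | Grade 4 row: stop infusion; next cycle if sponsor confirms | Permanent stop |
| Capillary leak syndrome with ventilator support | Grade 4 row: same | Permanent stop |
| Grade 3 anaphylaxis | Grade 3-or-worse row: half rate if improved within 3 days | Permanent stop |
| Grade 3 peripheral neuropathy | Grade 3-or-worse row: same | Permanent stop |
| Grade 3 eye toxicity | Grade 3-or-worse row: same | Permanent stop |
| Recurrent capillary leak syndrome | Capillary leak row: half rate once improved | Permanent stop |

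**Step 2. Is there a rule of precedence?** Neither 5.4 nor 7.6.1 cites the other. Section 9.6 does not settle it. It requires immediate discontinuation after a severe infusion-related reaction, which sides with 7.6.1 on anaphylaxis. For Grade 3 vision toxicity it asks only for interruption, which sides with Table 3.

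**Step 3. Skin toxicity and neuropathic pain.** Grade 4 is also Grade 3 or worse, so these reactions fall literally in two rows: restart at half rate without sponsor contact, or stop the infusion and ask the sponsor about the next cycle. Section 7.6.1 lists neither, so it cannot decide between them. The 5-week bracket could be attached to the last item only or to the whole list. The second reading does not work. For onset on day d, 5 weeks ends on day d + 35, which is day d of the next 35-day cycle, while the infusion is planned to end on Day 11. The instruction to stop the infusion would then come after that infusion was normally over.

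**Step 4. What precedence for the Grade 4 row would cost in dose.** Section 5.2.1 gives 48 mL per day for 10 mg/m², so 2 mL/h is 10 mg/m²/day and half rate is 5 mg/m²/day. Assumptions: full rate before onset, a 3-day interruption, and dose counted to hour 240 (10 days).

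| | Onset after 1 day | Onset after 5 days |
|---|---|---|
| Grade 4 row | 10 | 50 |
| Half rate to the end | 10 + 0 + 6×5 = 40 | 50 + 0 + 2×5 = 60 |
| 1 day at half rate, then full | 10 + 0 + 5 + 5×10 = 65 | 50 + 0 + 5 + 1×10 = 65 |
| Dose forgone (mg/m²) | 40 − 10 = 30 to 65 − 10 = 55 | 60 − 50 = 10 to 65 − 50 = 15 |

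Section 5.4 also allows the infusion to be prolonged up to the 100 mg/m² cap. Counted that way, the most that could be forgone is 100 − 10 = 90 or 100 − 50 = 50 mg/m².

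**The case against.** The Grade 4 row grants nothing by itself. No further cycle follows without the sponsor, whose own protocol lists both reactions as permanent stops. Table 3 is headed as recommended, two sections send the reader to 7.6, and dosing depends on acceptable clinical and laboratory findings (section 8). Life-threatening events reach the sponsor within 24 hours (9.3, 9.5.2.1). All of this stands and limits the risk. It does not reconcile the texts. The half-rate rows need no sponsor contact, and reporting a serious event is not a condition for restarting. On recurrence, the Grade 3-or-worse row agrees with 7.6.1 for an event at half rate, but not at full rate.

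On skin toxicity and pain the objection largely succeeds. A reader might infer that two equally valid rows apply. The documents do not support that: naming these reactions in a Grade 4 row would have little purpose if the broader row governed them, and the 5-week bracket directly follows the item that it most naturally qualifies. What remains is that the precedence is unstated.

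A reader might also infer larger dose differences from the sentence that "the infusion rate may be increased up to 3 mL/h (continuous infusion". At 15 mg/m²/day after one day at half rate, the totals by hour 240 would be 10 + 5 + 5×15 = 90 or 50 + 5 + 15 = 70 mg/m². That rate comes from the general paragraph above the table and depends on tolerance. The Grade 3-or-worse row itself goes no further than full rate.

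**Conclusion.** Table 3 and section 7.6.1 conflict for the six situations tabulated above. For anaphylaxis and ventilator-dependent capillary leak syndrome the conflict holds however the 5-week bracket is read. The overlap for skin toxicity and neuropathic pain is a secondary drafting point.

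Severity is minor. Sponsor contact stands before any next cycle under the Grade 4 row, life-threatening events are reported promptly, and wording alone resolves the matter. How often the conflict would arise cannot be derived, because the documents give no rates for these specific reactions at these grades under continuous infusion without IL-2. The dose figures rest on assumed onset and interruption times.

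Two stronger conclusions should not be drawn. Table 3 does not authorise re-exposure after anaphylaxis at Grade 4; it refers the question to the sponsor. Nor are the PK parameter calculations put at risk, since SAP 6.7 uses actual dose and sampling times.

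**What to change.** In Table 3:

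1. State that the permanent stops in 7.6.1 override every row. An override limited to the sponsor-contact option would leave Grade 3 anaphylaxis, Grade 3 neuropathy, Grade 3 eye toxicity and recurrent capillary leak syndrome unresolved.
2. Remove the next-cycle option for anaphylaxis and ventilator-dependent capillary leak syndrome.
3. State that the Grade 4 row takes precedence over the Grade 3-or-worse row for the reactions it names, and that the 5-week clause, left at 5 weeks, applies only to the residual category of other Grade 4 toxicity.

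This is wording in one table with a cross-reference, and it needs no extra patients, visits or procedures. Items 1 and 2 take away nothing that 7.6.1 does not already rule out. Item 3 has a price: a patient whose Grade 4 pain or skin toxicity improves quickly loses the rest of that cycle's dose, in the amounts shown in Step 4. The loss is larger with early onset, which is when section 6.1 expects neuropathic pain.
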